A Comparative Study on the Effect of Vagus Nerve Stimulation on Trapezius Trigger Points

May 2025

NCT Number: [NCT ID not yet assigned]

Study Identification

- Unique Protocol ID: BAU-MA25
- Brief Title: Effect of Vagus Nerve Stimulation on Trapezius Trigger Points
- Official Title: A Comparative Study on the Effect of Vagus Nerve Stimulation and Ischemic Compression on Trapezius Trigger Points
- Secondary ID: None

Study Status

- Record Verification Date: December 2024
- Overall Status: Active, not recruiting
- Study Start Date: January 15, 2025
- Primary Completion Date: May 15, 2025
- Study Completion Date: June 25, 2025 (Anticipated)

Sponsor/Collaborators

- Sponsor: None
- Responsible Party: Principal Investigator
- Investigator: [name] [name], Physiotherapy and Rehabilitation, Bahçesehir University
- Collaborators:
 - [name]. [name], Bahçesehir University
 - Assoc. [name], Istanbul Beykent Hospital

Oversight

- U.S. FDA-regulated Drug/Device/IND/IDE: No
- Human Subjects Review:
 - Board Status: Approved
 - Approval Number: 61351342/020-667

- Board Name: Üsküdar University Ethical Committee
- Board Affiliation: Bahçesehir University
- Contact: [name], [contact]
- Address: [name]

Study Description

Brief Summary

This randomized controlled trial aims to evaluate the efficacy of non-invasive vagus nerve stimulation (nVNS) compared to ischemic compression (trigger point massage) and exercise in treating trigger points in the upper trapezius muscle. Ninety participants aged 18-55 with at least two trigger points were randomly assigned to three groups: nVNS, ischemic compression, or exercise (control). Interventions were administered over 10 sessions (3 times per week). Outcomes included pain intensity (Visual Analog Scale, VAS), trigger point number, pain pressure threshold (algometer), neck function (Copenhagen Neck Functional Disability Scale, KBFÖS), well-being (WHO-5 Well-Being Index), and functional mobility. The nVNS group demonstrated statistically significant improvements in all outcomes compared to the other groups (p < 0.05).

Detailed Description

Myofascial pain syndrome (MPS) is characterized by trigger points-hyperirritable spots in skeletal muscle associated with pain, stiffness, and reduced function. The upper trapezius muscle is a common site for trigger points, contributing to neck pain and disability. Traditional treatments include ischemic compression and exercise, but non-invasive vagus nerve stimulation (nVNS) has emerged as a promising modality due to its ability to modulate pain pathways and autonomic function.

This study investigates whether nVNS is more effective than ischemic compression or exercise in reducing pain and improving function in patients with trapezius trigger points. Participants were randomized into three groups (n = 30 each):

- nVNS Group: Received auricular vagus nerve stimulation (10 Hz, 300 μ s, 20 minutes per session) using a non-invasive device adjusted to patient tolerance.
- Ischemic Compression Group: Received trigger point massage (30-90 seconds per point, 3 times per week).
- Exercise Group (Control): Performed isometric neck exercises, upper trapezius stretching, and chin tuck exercises.

Assessments were conducted pre- and post-intervention using validated tools. The nVNS group showed superior outcomes in pain reduction, trigger point resolution, pain threshold, neck function, and well-being (p < 0.05). Additional benefits included improved sleep quality, reduced stress, and enhanced mood, with no serious adverse events reported.

Keywords: Trigger Points, Vagus Nerve, Auricular Vagus Nerve Stimulation, Parasympathetic System, Ischemic Massage

Study Design

- Study Type: Interventional
- Primary Purpose: Treatment
- Study Phase: Not Applicable (Non-drug intervention)
- Interventional Study Model: Parallel Assignment
- Number of Arms: 3
- Masking: Single (Outcomes Assessor)
- Allocation: Randomized Enrollment: 90 (Actual)

Arms and Interventions

Arm 1: Vagus Nerve Stimulation (nVNS)

- Intervention Type: Device
- Description: Non-invasive auricular vagus nerve stimulation delivered bilaterally to the concha and tragus using a TENS-based device (10 Hz, 300 μ s, 20 minutes, 10 sessions over 4 weeks). Intensity was adjusted to patient comfort.
- Intervention Name: Auricular Vagus Nerve Stimulation

Arm 2: Ischemic Compression

- Intervention Type: Procedure
- Description: Manual trigger point massage (ischemic compression) applied to trapezius trigger points for 30-90 seconds per point, 3 times per week for 10 sessions.
- Intervention Name: Trigger Point Massage

Arm 3: Exercise (Control)

- Intervention Type: Behavioral
- Description: Standardized exercise program including isometric neck exercises, upper trapezius stretching, and chin tuck exercises, performed 3 times per week for 10 sessions.
- Intervention Name: Exercise Program

Outcome Measures

Primary Outcome Measures

- 1. Pain Intensity (VAS)
 - Description: Measured using the Visual Analog Scale (0-10), where 0 indicates no pain and 10 indicates worst possible pain.
 - Time Frame: Baseline and post-intervention (week 4).
- 2. Number of Trigger Points
 - Description: Count of active and latent trigger points in the upper trapezius muscle, assessed by palpation.
 - Time Frame: Baseline and post-intervention (week 4).
- 3. Pain Pressure Threshold (Algometer)
 - Description: Measured using a digital algometer (kg/cm²) at trigger point sites to assess pain sensitivity.
 - Time Frame: Baseline and post-intervention (week 4).

Secondary Outcome Measures

- 1. Neck Function (KBFÖS)
 - Description: Assessed using the Copenhagen Neck Functional Disability Scale, evaluating neck-related disability (0-30, higher scores indicate greater disability).
 - Time Frame: Baseline and post-intervention (week 4).
- 2. Well-Being (WHO-5)
 - Description: Measured using the WHO-5 Well-Being Index, a 5-item scale (0-25, higher scores indicate better well-being).
 - Time Frame: Baseline and post-intervention (week 4).
- 3. Functional Mobility
 - Description: Assessed through clinical tests of neck range of motion and mobility tasks.
 - Time Frame: Baseline and post-intervention (week 4).

Eligibility Criteria

• Ages Eligible for Study: 18 Years to 55 Years (Adult)

- Sexes Eligible for Study: All
- Accepts Healthy Volunteers: No

Inclusion Criteria

- Age 18-55 years.
- Presence of at least two trigger points (active or latent) in the upper trapezius muscle, confirmed by palpation.
- Ability to provide informed consent.

Exclusion Criteria

- History of cervical spine surgery or trauma.
- Neurological disorders (e.g., epilepsy, stroke).
- Pregnancy or breastfeeding.
- Use of pacemakers or other implanted electrical devices.
- Active infection or skin lesions at the stimulation site.
- Recent use of botulinum toxin or other trigger point injections.

Contacts/Locations

Contacts

- Primary Contact: [name] [name], [name], [contact]
- Secondary Contact: [name], [name]., [name], [contact]

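### Do three primary outcomes and two comparators at p < 0.05 give this trial a 19–25% chance of a false primary claim?

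*Protocol*

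**What the plan says.** The Primary Outcome Measures section of the Protocol lists three outcomes without ranking them: "Pain Intensity (VAS"), "Number of Trigger Points" and "Pain Pressure Threshold (Algometer"). Each is measured at baseline and week 4. There are three arms of 30.

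The Detailed Description puts the question this way: "This study investigates whether nVNS is more effective than ischemic compression or exercise in reducing pain and improving function". The Brief Summary states the aim as a comparison with the same two groups, but joins them with *and*.

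A significance threshold appears twice, each time in a sentence about results:

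- Brief Summary: "The nVNS group demonstrated statistically significant improvements in all outcomes compared to the other groups (p < 0.05").
- Detailed Description: "The nVNS group showed superior outcomes in pain reduction, trigger point resolution, pain threshold, neck function, and well-being (p < 0.05").

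The Protocol names no test and does not say whether tests are one- or two-sided. It does not say whether the p-values are adjusted, and it does not say how many comparisons must succeed. It states no familywise error rate.

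**The concern.** Three unranked primary outcomes and two comparators make six primary comparisons. The threshold shown is the usual single-test one, and the study question contains an *or*. A reader can easily conclude that any one of six results below 0.05 would count as a positive trial. On that rule, the 5% error rate attached to one test would not apply to the trial's main claim.

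The same threshold is also attached to the secondary outcomes, which brings the count to 12 comparisons. If this reading were right, nVNS could be declared superior on a primary outcome by chance far more often than the threshold suggests.

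**Working it through.** The Protocol gives no familywise error rate, so there is no stated figure to reproduce. The check has two parts: what the any-one rule would cost, and whether the Protocol contains that rule.

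**Inputs from the Protocol.** Three primary outcomes (Primary Outcome Measures), two comparators and 30 per arm (Detailed Description), and p < 0.05 (both descriptions).

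**Assumptions.** Two-sided tests, no true effect on any outcome, normal test statistics, and an equal correlation between outcomes that the Protocol does not give. It is varied here from 0 to 0.9.

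**Step 1: independent tests.** The chance of at least one false result is 1 − 0.95^6 = 1 − 0.735 = 26.5%. For 12 tests it is 1 − 0.95^12 = 46.0%, but that count includes secondary outcomes and is not an error rate for a primary claim.

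**Step 2: shared nVNS arm.** With equal arms and outcome SD σ, each contrast has variance 2σ²/30. The two contrasts on one outcome have covariance σ²/30, so they correlate at (1/30)/(2/30) = 0.5. Simulating the six tests with 1,000,000 draws per setting gives:

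| Outcome correlation | Any of six, either direction | Any of six, favouring nVNS | Any of six, after an omnibus three-group test per outcome | All six favouring nVNS |
|---|---|---|---|---|
| 0 | 24.8% | 13.0% | 11.9% | 0.000% |
| 0.3 | 23.7% | 12.0% | 11.5% | 0.001% |
| 0.5 | 22.0% | 11.0% | 10.7% | 0.007% |
| 0.7 | 19.2% | 9.6% | 9.5% | 0.036% |
| 0.8 | 17.4% | 8.7% | 8.5% | 0.08% |
| 0.9 | 14.9% | 7.4% | 7.2% | 0.15% |

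The 19–25% is therefore correct for one specific rule: six unadjusted two-sided tests, no omnibus gate, either direction counting, any single success enough, and correlations of 0 to 0.7. The study question is directional, and false findings in favour of nVNS run at about 10–13% over the same range. The rate depends heavily on the rule, so the next step is to see which rule the Protocol sets.

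**Step 3: the passages side by side.**

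- *Unadjusted.* Neither sentence with p < 0.05 says this. A bare p < 0.05 fits an adjusted or post-hoc-corrected p-value just as well.
- *Decision rule.* Both sentences are in the past tense and report what was found. Neither fixes in advance what would count as success.
- *Any one suffices.* The only textual support is the *or* in the Detailed Description. The Brief Summary has *and* for the same two comparators. Taken together, the two do not establish that one comparator is enough, and neither sentence says that one outcome is enough.

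**Step 4: the claim actually made.** The Brief Summary reports "statistically significant improvements in all outcomes compared to the other groups (p < 0.05"). On its natural reading this includes all six primary comparisons. A joint claim can be false only if at least one of the six null hypotheses is true, and it then requires that particular test to be significant. Its error rate therefore cannot exceed that of a single valid 5% test, whatever the correlation. With no effect anywhere it is far lower, as the last column shows. In addition, if all six p-values are below 0.05, Hochberg's step-up procedure rejects all six with familywise control under positive dependence.

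**The case for a change.** The strongest reply is that the number of primary outcomes, their equal rank and the wording of the question are all fixed in the Protocol, and that what makes a trial positive is a design matter. The joint result is something reported, not something required in advance. The Detailed Description repeats the claim for five outcomes only, leaves out functional mobility, and names no comparator in that sentence. A reader could therefore lift a single p < 0.05 and treat it as a confirmed primary finding. Even the milder variants in the table, about 10–13%, are well above the 2.5% that one two-sided test allows in favour of nVNS.

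Part of this stands. The Protocol writes down no success rule and no multiplicity method, and a clear statement of both would help the reader. But that is missing detail of the kind an SAP commonly supplies. It does not turn silence into a statement that p-values are unadjusted or that any one result will do.

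The remedies would not repair an error either. Requiring all six to succeed is already met by the reported result, on the reading above, so it would change no conclusion. Choosing Holm over Hochberg or a joint rule, once results are known, is a preference and cannot pre-specify anything.

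The phrase about the other groups could instead mean an omnibus three-group test. In that case the six-test model behind the 19–25% does not describe the analysis, and the reported claim is still joint across outcomes.

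**Conclusion.** The concern does not hold. The 19–25% is sound arithmetic for a rule the Protocol does not contain. It needs unadjusted two-sided tests, no gate, any one of six successes in either direction, and outcome correlations of 0 to 0.7. The Protocol reports success on all outcomes against the other groups. Read as all six primary comparisons, that claim is not inflated by multiplicity: below 0.1% under no effect anywhere for correlations of 0 to 0.8, and 0.15% at 0.9.

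This conclusion rests on that reading of the Brief Summary and on the SAP being the usual place for the multiplicity method. If a document showed that any single unadjusted success was to count, the figures in the table would apply.

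### The December 2024 verification date cannot support the outcome ranking as set before the start, and the sleep, stress and mood benefits correspond to no listed outcome

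*Protocol*

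**What the plan says.** The Protocol is headed May 2025. Its Study Status section gives "Record Verification Date: December 2024", "Study Start Date: January 15, 2025" and "Overall Status: Active, not recruiting". Study Design gives "Allocation: Randomized Enrollment: 90 (Actual").

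The Outcome Measures section lists three primary outcomes (VAS pain, number of trigger points, pressure pain threshold) and three secondary ones (KBFÖS, WHO-5, functional mobility), each at baseline and week 4. The Brief Summary names the same six in the same order but does not rank them; it begins "Outcomes included pain intensity (Visual Analog Scale, VAS), trigger point number, pain pressure threshold (algometer), neck function" and goes on to the other two.

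Both narrative sections report efficacy. The Brief Summary claims significance at the 0.05 level on every outcome. The Detailed Description says "The nVNS group showed superior outcomes in pain reduction, trigger point resolution, pain threshold, neck function, and well-being (p < 0.05"). Its next sentence adds sleep quality, stress and mood as further benefits, without a p-value, instrument or time point.

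Oversight records "Board Status: Approved" with an approval number but no approval date. The registry number is given as not yet assigned.

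**The concern.** Primary status supports a confirmatory claim only if it was fixed before the results were known. Here the ranking appears in one section only, in a text that also contains the results. The only date before the start anywhere in that text is the verification date, and the content around it shows that it cannot belong to the present wording. A reader looking for evidence of prespecification finds no valid date to rely on.

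The sleep, stress and mood statements raise a different problem. They are presented as effects of the intervention, yet they cannot be traced to a planned measure. If they are carried into a report, nothing in this text tells the reader how they were assessed or whether they were planned.

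**Working it through.** No power or error-rate formula applies, and the Protocol gives no figure to reproduce. The check is the order of dates, followed by a match of claims against listed outcomes.

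**Dates.** Inputs: verification in December 2024 (no day given), start on January 15, 2025 and primary completion on May 15, 2025, all from Study Status; and the schedule in the Brief Summary, "Interventions were administered over 10 sessions (3 times per week").

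- Verification to start: December 31 to January 15 = 15 days; December 1 to January 15 = 31 + 14 = 45 days. By the stated start date, none of the 90 could have been enrolled in December 2024.
- Earliest tenth session, assuming a first session on the start date and at most three sessions in each 7-day week: nine sessions fit in weeks 1 to 3, so the tenth falls no earlier than day 22, that is January 15 + 21 days = February 5, 2025.
- Verification to that date: 15 + 21 = 36 days to 45 + 21 = 66 days.
- End of December to stated primary completion: 31 + 28 + 31 + 30 + 15 = 135 days.

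The actual enrolment and the efficacy results therefore cannot have existed in December 2024. The February 5 figure depends on the assumptions above, but the conclusion does not: the start date alone settles it.

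**Other possible anchors for the ranking.** The May 2025 heading is later than the start. The board approval has a number but no date. The registry number is not yet assigned, so no earlier registration is pointed to. This text thus contains no valid date before January 15, 2025 for the ranking.

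**Claims against listed outcomes.**

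| Claimed in the Detailed Description | Listed outcome |
|---|---|
| Pain | VAS (primary) |
| Trigger points | Number of trigger points (primary) |
| Pain threshold | Algometer (primary) |
| Neck function | KBFÖS (secondary) |
| Well-being | WHO-5 (secondary) |
| Sleep quality | none |
| Stress | none |
| Mood | none |

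Five claims match a listed outcome and three do not. WHO-5 does not clearly fill the gap. It is listed as a single 0 to 25 well-being score, and well-being has already been named before the three extra benefits are added to it.

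**The case against.** The strongest reply is that no careful reader is misled. The text is headed May 2025, speaks of randomisation in the past tense and reports results, so it plainly postdates the start. Nothing in it says that the verification date dates the outcome list. On this view what remains is one stale administrative field, and correcting it is clerical. The extra benefits stand in their own sentence without a p-value and are not called planned or confirmatory.

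Much of this stands. The heading already shows that the wording is later than the start, and the date correction is minor in itself. But a later heading supplies no earlier date for the ranking; it confirms that the only pre-start date in the text has to be set aside. The separate sentence lowers the standing of the sleep, stress and mood claims, but still presents them as benefits of nVNS with no source.

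A reader might go further and infer that the outcomes, or their ranking, were chosen after the data were seen. The text does not support that. The Brief Summary and the Outcome Measures section name the same six outcomes, so no dropped or added outcome is visible between them. Results written into a narrative later do not show when the outcome list was set. Board approval is recorded, so a dated approved version may exist outside this text.

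**Conclusion.** The point holds in two limited parts.

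First, the December 2024 verification date, 15 to 45 days before the start, cannot apply to a text that reports 90 actual participants and efficacy results. It lends no support to the primary and secondary ranking as set before the start. Whether the ranking was in fact set earlier is open: it is neither shown nor refuted here.

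Second, three claimed benefits (sleep, stress, mood) match none of the six listed outcomes and have no stated measure or time frame.

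The date conclusion rests only on taking the stated start date as correct. No bias in the reported p-values can be quantified from this text, and none is claimed. The consequence concerns what the trial may conclude; no result needs recomputing on this account.

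**What to change.** 1. Remove the sleep, stress and mood claims, or label them post hoc and non-confirmatory and name the measure if there was one. The exception is a version approved before January 15, 2025 that lists them.
2. For the outcome ranking, cite the dated version approved before the start. If none can be cited, state that this text cannot establish that the ranking was prespecified, and make no confirmatory claim from it.
3. Correct the verification date as an administrative matter.

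The cost is a few words, one citation and one date. The downside is that the three extra claims, and possibly the ranking, lose confirmatory weight.

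### The protocol reports better sleep, less stress and better mood as benefits, but none of the three is among its six defined outcomes

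*Protocol*

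**What the plan says.** The Brief Summary lists what was measured. The list opens "Outcomes included pain intensity (Visual Analog Scale, VAS), trigger point number, pain pressure threshold (algometer), neck function" and closes "well-being (WHO-5 Well-Being Index), and functional mobility". The Outcome Measures section repeats the same six, as three primary outcomes (VAS pain, number of trigger points, pressure threshold) and three secondary outcomes (KBFÖS neck function, WHO-5 well-being, functional mobility). Each has a description and a time frame of baseline and week 4.

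The Detailed Description sets a comparative question: "whether nVNS is more effective than ischemic compression or exercise in reducing pain and improving function". It then gives the main result: "The nVNS group showed superior outcomes in pain reduction, trigger point resolution, pain threshold, neck function, and well-being (p < 0.05"). The next sentence begins "Additional benefits included improved sleep quality, reduced stress, and enhanced mood" and closes with a statement that there were no serious adverse events.

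**The concern.** The last of those sentences presents three effects as benefits, and the document never defines any of them as something to be measured. They directly follow the superiority result, in a paragraph that begins by saying validated tools were used before and after treatment. A reader will therefore take them as trial findings.

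Two things are at stake. First, the trial has two comparison arms, and both were treated. Without a group comparison, a reported improvement in sleep, stress or mood cannot be told apart from change that also occurred under ischemic compression or exercise. Second, an outcome list lets a reader see what was looked for and judge what was found. Favourable effects from outside the list, with no record of what else was asked, take away that check. The protocol gives masking for the outcomes assessor only. If these effects were self-reported, which is an assumption because the source is not stated, they would also be open to participants' expectations.

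**Working it through.** The protocol gives no figure to reproduce here, so the check sets each claimed effect against the outcome lists.

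| Favourable effect in the Detailed Description | In the Brief Summary list? | In Outcome Measures? | Covered by p < 0.05? |
|---|---|---|---|
| Pain | Yes | Primary 1 (VAS) | Yes |
| Trigger points | Yes | Primary 2 | Yes |
| Pain threshold | Yes | Primary 3 (algometer) | Yes |
| Neck function | Yes | Secondary 1 (KBFÖS) | Yes |
| Well-being | Yes | Secondary 2 (WHO-5) | Yes |
| Sleep quality | No | No | No |
| Stress | No | No | No |
| Mood | No | No | No |

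**Counts.** Outcomes defined: 3 primary + 3 secondary = 6, the same six as in the Brief Summary. Favourable effects named: 5 + 3 = 8. Effects with no listed outcome and no p-value: 3/8 = 37.5%. (The sixth listed outcome, functional mobility, is not named in these two sentences and does not affect the count.)

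**Could a listed scale be the source?** Only the two questionnaire scores are candidates.

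- WHO-5: "Measured using the WHO-5 Well-Being Index, a 5-item scale (0-25, higher scores indicate better well-being"). This is one total score. No item or subscale is declared as an outcome, and its result is already reported as well-being in the preceding sentence. Effects described as additional to that result are, on the document's own wording, something else.
- KBFÖS: "evaluating neck-related disability (0-30, higher scores indicate greater disability"). Again this is one total score with no item-level outcome, and its result is already reported as neck function.

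The other four outcomes (VAS pain, trigger point count, pressure threshold, range of motion and mobility tasks) do not concern sleep, stress or mood.

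**Could part of the list be missing?** The Outcome Measures section runs from primary outcome 1 to secondary outcome 3 and straight on to Eligibility Criteria, with no gap or redaction mark.

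**The case against.** The strongest reply is that the document does not put these effects into its comparative conclusion. The p-value and the word for superiority belong to the five named outcomes. The sentence in question sets itself apart as additional, names no group and gives no test. That is a fair reading, and it limits the point: the protocol does not claim statistical significance for sleep, stress or mood. It still calls them benefits, directly after the nVNS result, and gives no basis for doing so.

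A second reply is that the lists need not be exhaustive. The Brief Summary says what the outcomes included, and an analysis plan that is not shown may define exploratory measures. This also stands in part: the document supports saying that the three are not listed, not that they were never measured. But an unseen plan would not remove the mismatch between the results this protocol states and the outcomes it defines.

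Third, the general statement about validated tools before and after treatment could cover these effects. It names no tool for any of them, so it gives a reader nothing to check.

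Fourth, WHO-5 items might touch on such states. The protocol does not list the items, so this cannot be settled from it. Even if one did, no item-level outcome is declared.

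Finally, the 37.5% counts phrases. It measures no bias or loss of precision and should be read only as the extent of the mismatch.

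**Conclusion.** The concern holds. None of the three claimed benefits (0 of 3) matches an outcome in either list, and none has a stated instrument, time point, comparator or p-value. They make up three of the eight favourable effects named in the Detailed Description.

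This rests on the document's own definitions of its outcomes. It does not assume that the data are false or were not collected. Design, sample size and the reported results for the six listed outcomes are unaffected. The statement should be corrected because it presents unsupported effects as findings of a comparative trial, but it does not undermine the primary analysis.

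**What to change.** Remove sleep quality, stress and mood from the stated results. The safety statement in the same sentence can remain.

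If the three were in fact collected, the authors should instead state the instrument and the time points, report the results for all three groups, and label them exploratory and outside the listed outcomes. They should not be worded as benefits shown for nVNS. This route keeps any collected results visible.

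Removal is a text edit that needs no data. The alternative needs group results that this document does not contain. Either way, the cost is a slightly less favourable narrative.

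### Is the week-4 pressure threshold comparison distorted because trigger points that resolve might not be measured?

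*Protocol*

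**What the plan says.** The Protocol, under Primary Outcome Measures, lists pain intensity, the number of trigger points and the pressure pain threshold, each at baseline and week 4. Item 3, the threshold, is "Measured using a digital algometer (kg/cm²) at trigger point sites to assess pain sensitivity". Item 2 is a "Count of active and latent trigger points in the upper trapezius muscle, assessed by palpation". The Inclusion Criteria require "Presence of at least two trigger points (active or latent) in the upper trapezius muscle, confirmed by palpation".

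The Detailed Description reports that the stimulation arm had "superior outcomes in pain reduction, trigger point resolution, pain threshold, neck function, and well-being". Each arm has 30 participants, and the enrolment of 90 is marked as actual.

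The text does not say which sites are read at week 4, how many are read, how they are combined into one value per participant, or what is recorded when no point remains.

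**The concern.** Items 2 and 3 concern the same objects. If treatment makes trigger points disappear, and the threshold is read only where a trigger point exists on the day, then the sites available at week 4 are themselves a result of treatment. The best-improved sites leave the average, a participant whose points have all resolved has no value, and both losses are larger in the arm that works better. The contrast would then be between the residual, more sensitive points in each arm and no longer between the groups as randomised.

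At stake would be an attenuated estimate and unequal missing data on one of three primary outcomes. Entry on as few as two points makes a participant with none left plausible, and the reported difference in resolution between arms makes unequal loss plausible.

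**Working it through.** **No plan figure to reproduce.** The Protocol gives no mean, SD, effect size, resolution rate or power for the threshold. The only arithmetic available, 3 × 30 = 90, agrees. The rest is a reading of the text, followed by two illustrations on assumed inputs.

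**The text, side by side.**
- Item 3 places the algometer where the trigger points are, at two visits. It contains no rule that drops a site.
- Item 2 is a count at each visit. It does not follow individual baseline points and says nothing about where the algometer goes.
- Reading A: the baseline locations are read again at week 4. Every participant has at least two such locations by the inclusion rule, so every assessed participant has a value and nothing is conditioned on response.
- Reading B: only points palpable at week 4 are read. The comparison is then selected on response.

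The wording permits both. Reading A is the usual meaning of a paired baseline and follow-up measurement.

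**Illustration 1: participants with no point left under reading B.** With k points, each resolving independently with probability r, the share is r^k and the expected number per arm is 30 × r^k.
- k = 2: r = 0.2 gives 4% (1.2 of 30); r = 0.5 gives 25% (7.5); r = 0.8 gives 64% (19.2).
- k = 4: r = 0.2 gives 0.2% (0.0); r = 0.5 gives 6% (1.9); r = 0.8 gives 41% (12.3).

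**Illustration 2: the arm difference under each reading.** Assumed: two arms of 30, four sites each; baseline mean 2.5 kg/cm², between-person SD 0.45, between-site SD 0.4; gains of 1.0 and 0.5, so a true difference of 0.50; week-4 noise SD 0.4. A point persists if its week-4 threshold plus a palpation error lies below a cut-off. A small palpation error ties resolution closely to threshold; an SD of 5 makes the two nearly unrelated. There were 3,000 runs per row.

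| Cut-off | Palpation error SD | Difference, fixed sites | Difference, still-palpable sites | No point left, better vs other arm |
|---|---|---|---|---|
| 3.0 | 0.3 | 0.49 | 0.19 | 41% vs 15% |
| 3.0 | 0.8 | 0.50 | 0.34 | 27% vs 11% |
| 3.0 | 5 | 0.50 | 0.50 | 9% vs 6% |
| 3.5 | 0.3 | 0.50 | 0.27 | 15% vs 3% |
| 3.5 | 0.8 | 0.50 | 0.38 | 11% vs 3% |
| 3.5 | 5 | 0.49 | 0.49 | 6% vs 5% |
| 4.0 | 0.3 | 0.50 | 0.36 | 3% vs 0% |
| 4.0 | 0.8 | 0.51 | 0.42 | 3% vs 0% |
| 4.0 | 5 | 0.50 | 0.49 | 5% vs 3% |

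Reading A recovers the true difference in every row. Under reading B the estimate is 0.19 to 0.36 when resolution is closely tied to threshold, 0.34 to 0.42 when loosely tied, and 0.49 to 0.50 when nearly unrelated. Where there is bias, it shrinks the advantage of the arm with more resolution.

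**The case for a change.** The strongest argument for a change is that this is a primary outcome and that where the instrument is placed is settled when the data are collected. An analysis plan cannot recover readings that were never taken, so the gap cannot simply be left to a SAP. The assessor palpates again at week 4 for item 2, which makes reading only the points found that day a natural habit, and the Protocol mentions no marking or mapping of baseline sites.

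Much of this stands. The site of measurement belongs in the outcome definition, and the text leaves it open; only the averaging over sites and the handling of missing values could reasonably sit in a SAP. What does not stand is the step from an open wording to a biased comparison. That step needs reading B, which the Protocol nowhere states, and a close link between palpated resolution and algometer threshold, on which it gives no data. The same argument also limits the remedy: if resolved sites were skipped, rewording the outcome now would not bring the readings back.

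**Conclusion.** No change to the plan is called for. The gap is real but is one of missing detail: on the ordinary paired reading, with baseline sites read again at week 4, the outcome is sound and the comparison remains one between randomised groups. The harm exists only under the other reading. Its size then runs, on assumed inputs, from none to an estimate of 0.19 against a true 0.50 kg/cm². No power loss can be attributed to this trial, because the Protocol gives none of the quantities needed.

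Where bias arises in these simulations, it works against the arm with more resolution. The Protocol reports stimulation as superior on both resolution and threshold, so this mechanism would not account for that reported advantage. With enrolment complete and results already described, the report of the threshold result is the place to say which sites were read at week 4. If only persisting points were read, it should also give the number per arm with none left and label the result as conditional on persisting points. That is a matter of reporting and does not alter the design or the analysis.

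This conclusion rests on the paired reading being the one followed, which the document permits but does not confirm.
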